## **2-Parent Consent Procedures:**

If the parents are married, written consent may be obtained from one parent only. If the parents are not married, written consent will be obtained from: 1) the custodial parent if only one parent has legal custody, or 2) from both parents if they share legal custody for medical decision-making. For unmarried parents, signature of one parent will suffice if the other parent is deceased, unknown, incompetent, or not reasonably available. When signature of both parents is required, written consent will be obtained in-person from at least one parent. When the second parent is unable to attend the consent process conference in person, the following telephone process to obtain written consent will be used.

**Telephone Consent Procedures:** The unavailable parent will be provided with a copy of the consent form, usually by fax, email, or hard copy mail. Once the consent form is received, an Investigator authorized to obtain consent will arrange for a telephone call with the parent in the presence of a witness to review study and the consent form and to answer any questions. If the parent cannot arrange for a witness in his/her location, the consenting investigator will have a witness present for the teleconference at NIH. Once the parent agrees to his/her child's participation, the parent and witness (if present with the parent) will sign and date their copy of the consent form. The Investigator will enter a note documenting the consent process in the Medical Record. The 2nd parent will return their signed copy to the Investigator. Once the copy with the parent signature is received, the Investigator and witness (if present at NIH) will sign and date the 2nd parent consent form, place the original copy with all signatures in the Medical Record, retain a copy for research records, and mail a copy to the parent.

### **Capacity Assessment:**

#### **ADULT SUBJECTS**

Adult subjects in this protocol will be evaluated by HSPU/ACAT to determine, based on a protocol specific capacity assessment, if the subject has capacity to give informed consent. In all cases involving a guardian or an outside DPA (Durable Power of Attorney), the investigator will have the NIH legal department review the guardianship or DPA papers for authorization of research prior to consenting process.

- 1) If HSPU/ACAT determines that the subject has capacity, informed consent will be obtained by a designated investigator with consent monitoring by HSPU.

- 2) If HSPU/ACAT determines that the subject lacks capacity to give informed consent, and has a legal guardian, the HSPU will conduct an assessment of surrogate understanding. Once understanding by the subject's legal guardian has been established, an investigator will obtain informed consent from the subject's legal guardian and HSPU will monitor the consent/assent process.
- 3) If HSPU determines that the subject lacks consent capacity and there is no legal guardian, the PI has 3 options:
  - A. If HSPU determines that the subject lacks capacity to provide informed consent, and if the subject has a Durable Power of Attorney (DPA) for health care, this DPA may be invoked by the medically responsible investigator or an investigator with credentials to obtain informed consent under this protocol. HSPU will conduct an assessment of surrogate understanding. Once understanding by the DPA has been established, the designated investigator will obtain informed consent from this DPA with HSPU monitoring the consent/assent process.
  - B. If HSPU determines that the subject lacks capacity to give informed consent and has no guardian or DPA, HSPU will determine if the subject understands the meaning and intent to assign an NIH DPA. The NIH DPA will be invoked by the medically responsible investigator or by an investigator with credentials to obtain informed consent under this protocol. HSPU will perform an Assessment of Surrogate Understanding. An investigator will then obtain informed consent from the NIH DPA, and assent from the subject, with HSPU monitoring the process.
  - C. If HSPU determines that the subject lacks capacity to give consent, the subject does not have a guardian or DPA and is unable to appoint an NIH DPA, then a Next of Kin surrogate may be appointed as outlined in MAS 87-4. ACAT will perform an Assessment of Surrogate Understanding. An investigator will obtain consent from the surrogate and assent from the subject with HSPU monitoring the process.

## **15. DATA AND SAFETY MONITORING**

### **15.1 Study Monitor**

This protocol will utilize a Safety Monitoring Committee (SMC) to review AEs and safety reports. The Safety Monitoring Committee will be composed of:

[name] is the Program Director of the Division of Clinical Research, NINDS. He is a board-Certified neurologist with extensive clinical trial experience. [name] is a board-certified neurologist and a member of [name] research section at NIH. She has extensive neurology experience.

The monitoring plan will include SMC review once six subjects have completed the treatment phase (Period 1 and Period 2) of the study. Thereafter, the SMC will review safety data, including seizure frequency, toxicity reports, neuropsychological and mood testing, laboratory tests, EEG, ECG and clinical examination once per year until the end of the trial.

Results will be reported to the Principal Investigator, IRB, and NINDS Clinical Director. Data review will be blinded, and no interim analysis is planned.

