In a Phase II double-blind, placebo-controlled study in 110 adults with mild cognitive impairment, oral administration of 600 mg t.i.d. for 8 weeks significantly improved attention, reaction time, visual information processing, and working memory (Froestl et al., 2004, Tomlinson et al 2004). No clear drug-related serious adverse events or drug related effects on cardiovascular or laboratory variables were reported (Froestl et al 2004). One patient had a syncopal episode; the patient had experienced a similar episode two years before starting SGS-742 treatment. One patient had AST elevation present at screening that did not worsen during the study, and persisted afterwards. One patient had an eye hemorrhage attributed to concomitant warfarin use. Mild to moderate nonspecific and non-dose-related adverse events included headache, tiredness, diarrhea, nausea and vomiting, sleepiness and dizziness. There was no difference in incidence between patients on active drug and placebo, except possibly for nausea and dizziness, which occurred in 7-10% of patients on active drug (Investigator's Brochure). All adverse events resolved fully and spontaneously. The drug has not yet been used in children.

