#### **3.2 Inclusion Criteria (See checklist Appendix 1)**

- 4-hydroxybutyric aciduria (gamma-hydroxybutyric aciduria) on two separate tests.
- Documented succinic semialdehyde dehydrogenase enzyme deficiency.
- Patients must have clinical features consistent with SSADH deficiency including developmental delay especially deficit in expressive language, hypotonia, ataxia, seizures, and other neuropsychiatric symptoms including sleep disturbances (45%), attention deficit (45%), anxiety (27%), obsessive-compulsive disorder (25%), and autistic traits (25%).
- During the study, women of child-bearing potential must use a reliable method of birth control until one month after the final drug taper is complete.
- Patients will be 4 years or older.
- Based on HSPU/ACAT evaluation must meet one of the following criteria:
  - subject has capacity to consent
  - subject has a documented legal guardian to provide consent
  - subject lacks capacity and no legal guardian but HSPU determines 1) the subject has a DPA, or 2) the subject has capacity to designate an NIH DPA, or 3) a Next of Kin surrogate may be appointed as outlined in MAS 87-4.

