##### 4.1.1 Study Phases (see Study Schedule Appendix 2):

- Screening (1-3 days)—outpatient. May be combined with baseline visit.
- Baseline visit (1 - 3 days)—inpatient or outpatient. The first dose of study pills will be administered at the NIH. The patient will stay for 30 – 90 minutes following the first dose. The patient will be permitted to return to local accommodations overnight and return 12 - 24 hours after the first dose to be assessed for any skin reactions, and then discharged home.
- Titration one: 9 - 15 days (titration is 9 days and if they only get one or two doses on day one they will have an additional day of drug titration).

Phase 1 (six months +/- 2 weeks of SGS-742 or placebo)—during phase one there will be regular communication, at least once every two weeks, with patients/families by phone and/or the clinical trial database. If indicated, based on reports during these regular communications, an outpatient visit will be arranged at NIH or with a local provider for safety monitoring or pregnancy testing. If this is to be done by local providers, we will have patients designate the local provider in advance. We will contact the local provider and arrange for payment of any visits or testing by the NIH and also document a plan in the progress notes for how individual providers will communicate findings and test results. We will request local providers provide written documentation of outpatient visits and pregnancy testing results by facsimile to include in the NIH patient medical record.

- End of phase 1 testing: (At 6 mo +/-2 weeks of phase 1) inpatient or outpatient 3 day evaluation including: EEG, TMS, neuropsychological tests, blood and urine tests, and optional LP, MRI/MRS.
- Washout 9 weeks (+/- 2 weeks), including 9 days to taper and discontinue phase I medication, at least 7 weeks medication free and titration to phase 2 medication 9 - 15 days (**taper is 9 - 15 days and if they only get one or two doses on day one they will have an additional day of drug taper**).

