## **15.2 Criteria for stopping the study**

New enrollment will be halted if a serious adverse event, as determined by the SMC, occurs in a patient found to be on active treatment after breaking the blind occurs. The study will not be restarted until reviewed by the IRB. The study may be stopped if in the judgment of the SMC there is evidence of Grade 3 toxicity on the NCI CTC.

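### The first scheduled safety committee review waits for six patients to finish both periods, with no calendar limit, so committee review of accumulating safety data comes late and slips further with dropout

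*Combined protocol and SAP*

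**What the plan says.** - **Timing (Section 15.1).** The plan is an "SMC review once six subjects have completed the treatment phase (Period 1 and Period 2) of the study". After that the Safety Monitoring Committee (SMC) looks at safety data "once per year until the end of the trial". No latest date is set for the first review, and no reason is given for the number six.
- **Blinding (Section 15.1).** "Data review will be blinded, and no interim analysis is planned".
- **Stopping (Section 15.2).** Enrolment halts for a serious adverse event (SAE), as judged by the SMC, that "occurs in a patient found to be on active treatment after breaking the blind occurs". The SMC may also stop the study on its judgement of Grade 3 toxicity.
- **Event routing (Sections 8 and 17).** SAEs temporally associated with the drug go to the independent safety monitor (ISSM) within 48 hours. Non-serious events reach the ISSM at IRB continuing review and at an annual SMC meeting. Section 17 holds seizures and related emergency care to continuing review.
- **Population.** Section 1.4 says "The drug has not yet been used in children"; Section 3.2 says "Patients will be 4 years or older".
- **Period lengths (Section 4.1.1).** "Titration one: 9 - 15 days"; "Phase 1 (six months +/- 2 weeks of SGS-742 or placebo"; a washout of nine weeks, give or take two, with a 9-day taper and at least seven drug-free weeks; then a second titration and a second six-month period.

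**The concern.** A standing committee is useful for patterns that no single case report shows: a rise in seizures, drift in laboratory values, behavioural change, or a run of mild events. Here its first scheduled look depends on patients finishing more than a year of study participation. If recruitment runs at even a moderate pace, most patients are randomised before that look, so it can do little for new entrants.

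The trigger also moves the wrong way. A patient who leaves because the drug is poorly tolerated does not advance the count and, if leaving before three months of the second period, is replaced (Section 3.1). Worse tolerability therefore means a later first review.

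Seizures show what is at stake. They are a background feature of the disease (45% in the Introduction), they appear at high doses in the animal toxicology of Section 7.1, and emergency seizure care is held to continuing review. A drug-related increase could pass for the underlying disease until somebody looks at the accumulated data.

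**Working it through.** **Inputs.** From Section 4.1.1: each titration 9 to 15 days; each period six months ± 14 days; washout 63 ± 14 days, containing a 9-day taper and at least 49 drug-free days. Six months = 6 × 30.4375 = 182.6 days. From Section 3.1: 22 enrolled for 16 completers. Accrual is not stated, so 0.5, 1 and 2 patients per month are assumed.

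**Step 1: first dose to end of Period 2.** Titration + Period 1 + washout + titration + Period 2:

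- Earliest: 9 + 168.6 + (9 + 49) + 9 + 168.6 = 413 days = 13.6 months.
- Nominal: 9 + 182.6 + 63 + 9 + 182.6 = 446 days = 14.7 months.
- Latest: 15 + 196.6 + 77 + 15 + 196.6 = 500 days = 16.4 months.

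Section 4.1.1 can be read as placing the second titration inside the washout. The nominal figure is then 437 days (14.4 months) and the latest 485 days (15.9 months). The earliest is unchanged, since 9 + 49 + 9 = 67 days fits within the 77 allowed.

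**Step 2: check against the plan's overall duration.** Section 4.1 states 16 to 21 months. Adding screening and baseline (2 to 6 days), the final taper (9 to 15 days) and the final visit (28 to 49 days later) gives 413 + 2 + 9 + 28 = 452 days (14.9 months) to 500 + 6 + 15 + 49 = 570 days (18.7 months). The component sums run shorter than the stated range, so Step 1 does not exaggerate the delay.

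**Step 3: how far enrolment has gone.** Suppose the first patient starts at month 0, accrual is even at rate *a*, and the first six all complete. The sixth starts at 5/*a*, so the review falls at 5/*a* + 14.7. Randomised by then: 1 + the whole part of (*a* × review month), capped at 22.

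| Accrual per month | First review (month) | Randomised of 22 |
|---|---|---|
| 0.5 | 10 + 14.7 = 24.7 | 13 |
| 1 | 5 + 14.7 = 19.7 | 20 |
| 2 | 2.5 + 14.7 = 17.2 | 22 |

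At 1 per month, the range of 13.6 to 16.4 months gives 19 to 22 randomised.

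**Step 4: dropout.** Planning 22 for 16 implies 6/22 = 27% loss. At that rate six completers need 6 × 22/16 = 8.25 starters. If the sixth completer is the eighth patient, at 1 per month the review falls at 7 + 14.7 = 21.7 months, with all 22 randomised.

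**Step 5: an earlier trigger.** Titration plus Period 1 takes (9 + 182.6)/30.4375 = 6.3 months. Take the earlier of 5/*a* + 6.3 and month 12, with no discontinuations:

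- 0.5 per month: month 12 (the backstop applies), about 7 randomised.
- 1 per month: month 11.3, about 12 randomised.
- 2 per month: month 8.8, about 18 randomised.

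**Step 6: what a small review can show.** With six patients exposed to active drug, the chance of at least one event is 1 − 0.95⁶ = 27% at a 5% rate, 47% at 10% and 74% at 20%. Zero events in six leaves a one-sided 95% upper limit of 1 − 0.05^(1/6) = 39%. One-sided exact McNemar power with six full pairs is 0.8% for 30% versus 5%, and 8.4% for 50% versus 5%. No formal test is realistic.

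**Step 7: the sections side by side.** Sections 8 and 17 rely on an annual SMC meeting; Section 15.1 starts annual review only after six completers. Section 15.2 needs the SMC to judge an SAE; Sections 8 and 17 route SAEs to the ISSM, the IRB and the Clinical Director, and none says how or when they reach the SMC between meetings. Section 17's deferral of emergency seizure care does not say whether it also applies to the 48-hour ISSM route.

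**The case against.** The strongest reply is that the SMC is only one layer. SAEs reach the ISSM within 48 hours whether or not thought related. Families are contacted at least every two weeks. Section 8 has patient-level toxicity rules. Section 8.1 brings Grade 3 toxicity, marked laboratory changes and new EEG or ECG findings to the safety monitor, and allows unblinding even for non-serious events. All adverse events are summarised at IRB continuing review. This stands. A reader might infer that a treatment-related signal cannot be seen in time; the documents do not support that for individual serious events.

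Nor do they support reading the Section 15.2 SAE rule as unworkable under blinded review: that rule operates after the blind is broken for the patient concerned. Section 15.1 also says blinded, not pooled. Patient listings by period could show events clustering in one period, though not which treatment was given.

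A further reply is that an earlier look holds little information. Six patients at the end of Period 1 means about three on active drug. At 15% versus 5%, the chance of any event is 1 − 0.85³ = 39% among three active patients and 1 − 0.95³ = 14% among three on placebo, which cannot separate the arms. This also stands, and it limits the claim to descriptive oversight.

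Two points soften the timing. Slow recruitment is plausible in a rare disease; at 0.5 per month 13, not 20, are randomised, although the review then waits about 25 months. And Section 8 lets patients who stop the drug stay in follow-up; whether they count towards the six is not stated.

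**Conclusion.** The concern holds for the committee's scheduled review of accumulating data, not for single serious events. The first review falls 13.6 to 16.4 months (nominally 14.7) after the sixth completer's first dose, has no calendar limit, and moves later with dropout. At an assumed 1 patient per month or faster, about 20 or more of 22 patients are randomised by then; this rests on even accrual and on the first six completing. Continuing review passes non-serious events to the IRB and ISSM in the meantime, but no section assigns anyone a summary by treatment. The inconsistency over the annual meeting and the missing SAE route to the SMC need no assumption about accrual. The change should be made because the drug is new to children and the wording is cheap to alter. It does not invalidate the design.

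**What to change.** 1. **Timing.** Change Section 15.1 so that the first SMC review falls at the earlier of (a) six treated patients having reached the end of Period 1 or discontinued, or (b) 12 months after the first patient's first dose, and annually after that. Counting discontinuations stops poor tolerability from delaying the review. The end of Period 1 is also when the first scheduled on-treatment blood tests and EEG become available.
2. **Routing.** Reconcile Sections 8, 15.1, 15.2 and 17: when the SMC meets, how and when SAEs reach it between meetings, and whether the seizure deferral applies to the ISSM as well as the IRB.
3. **Treatment codes (secondary).** State that the SMC may obtain treatment-coded safety tables from the NIH Pharmacy, which holds the schedule, in a closed session while investigators stay blinded. The tables would cover adverse events, seizures, laboratory, EEG and ECG. Leave out neuropsychological scores, which are a primary efficacy outcome as well as a safety outcome (Sections 9.1 and 9.3); efficacy then stays masked and no alpha is spent.

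**Cost.** Plan wording and one earlier meeting. If coded tables are used, a single broken blind would reveal the code to SMC members for every patient in the tables, which is why item 3 is secondary.

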## **15.2 Criteria for stopping the study**

New enrollment will be halted if a serious adverse event, as determined by the SMC, occurs in a patient found to be on active treatment after breaking the blind occurs. The study will not be restarted until reviewed by the IRB. The study may be stopped if in the judgment of the SMC there is evidence of Grade 3 toxicity on the NCI CTC.

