## **8. SUBJECT SAFETY MONITORING**

Patients will be monitored by CES Staff, including PI, nurse practitioner and fellows, and by [name], a board-certified pediatric neurologist, who is a

special volunteer with clinical privileges at NIH, and has the world's largest experience with SSADH deficiency.

[name] will serve as Independent Study Safety Monitor (ISSM). [name] is a Board-Certified Neurologist with Fellowship training in Movement Disorders who is conducting clinical research with [name].

The ISSM will serve as the IND sponsor's medical monitor and will make the final determinations of relatedness of safety events to the investigational product on behalf of the sponsor (NINDS). The ISSM will review serious adverse events, and serious unanticipated problems. SAEs that are at least temporally associated with the use of the study drug (whether assumed to be related or not) will be given to the ISSM immediately, but no later than 48hrs from the time the PI learns of an event. The PI will record nonserious AEs and report them to the ISSM at the time of 1) IRB continuing review and 2) the annual Safety Monitoring Committee's annual meeting. The ISSM will review these reports and provide feedback to the PI and NINDS in a timely manner.

Patients will be monitored carefully by CES clinicians for any change in their clinical status during clinic visits and self-report during phone and computer contact. Intervention will be determined by the independent subject safety monitor and may include consultation, additional studies, or withdrawing the patient from the protocol.

Parameters to be monitored include seizure frequency, neurological examination, fluctuations in cognitive and behavioral features. Specific drug-related side effects to be monitored include headache, tiredness, nausea and vomiting, sleepiness and dizziness.

Patients who cannot tolerate the study drug will be taken off of it. Following review and approval by the Independent Subject Safety Monitor, patients who stopped taking the study drug can remain in the study and complete follow-up visits and assessments.

Females who become pregnant will stop the study drug however will remain in the study and can be followed under the protocol. They will not complete any assessments that pose risk to the pregnancy or fetus but can do other non-invasive procedures such as neuropsychological testing. They will be followed until the end of the study or pregnancy outcome, whichever is later.

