Patients will be removed from the study if they are unable to cooperate, or have an alteration in clinical status needing medical intervention. Patients may withdraw from the trial at any time at their own request. The Investigators may withdraw a subject for safety or behavioral reasons.

Toxicity will be graded according to the NCI Common Terminology Criteria for Adverse Events (appendix 2). Dose limiting toxicities will be considered any NCI grade 3 toxicity felt to be probably or definitely related to study medication; grade 4 or 5 toxicity judged to be possibly, probably or definitely related to study medication by the safety monitor.

In the event of a Grade 3 toxicity felt to be probably or definitely related to study medication by the study investigator or safety monitor, one-step dose reductions will be initiated until the toxicity resolves. If NCI Common Terminology Grade 4 toxicity is felt to be possibly, probably or definitely related to study medication by the study investigator, the patient will be withdrawn from the study medication. All dose changes and/or dose interruptions will be recorded on case report forms.

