### **8.1 Criteria for Breaking the Blind and Premature Termination or withdrawal**

Criteria to be used to decide whether a report or test result requires intervention include Grade 3 NCI CTC toxicity, a laboratory test twice the upper limit of normal, an abnormal finding on EEG or ECG not present at baseline. Intervention will be determined by the safety monitor and may include consultation, additional studies, or withdrawing the patient from the protocol.

The blind for an individual may need to be broken even for non-serious, expected, or unrelated AEs or as requested by local regulatory authorities or where, in the view of the safety monitor, knowledge of the identity of the study drug is essential to appropriately manage an adverse event.

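### Both trial-level safety rules belong to the SMC, but no stated route brings it a serious adverse event or the patient's assignment between scheduled reviews

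*Combined protocol and SAP*

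**What the plan says.** Section 15.2 has two trial-level rules. The first is mandatory: "New enrollment will be halted if a serious adverse event, as determined by the SMC, occurs in a patient found to be on active treatment", with the wording going on to make the finding follow from breaking the blind. The second is discretionary: "The study may be stopped if in the judgment of the SMC there is evidence of Grade 3 toxicity on the NCI CTC". Restart after a halt needs IRB review.

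Section 15.1 gives the SMC a general remit over adverse events and safety reports. Its first stated review is "SMC review once six subjects have completed the treatment phase (Period 1 and Period 2) of the study", followed by yearly reviews. It adds: "Data review will be blinded, and no interim analysis is planned".

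Section 8 sets the fast SAE route. Events at least temporally associated with study drug "will be given to the ISSM immediately, but no later than 48hrs from the time the PI learns of an event". Section 17 repeats the 48-hour rule and separately requires written SAE reports to the IRB and Clinical Director within 7 days. Emergency treatment of seizures is held for continuing review.

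At patient level, section 8 states: "Intervention will be determined by the independent subject safety monitor and may include consultation, additional studies, or withdrawing the patient from the protocol". For related Grade 3 toxicity, "one-step dose reductions will be initiated until the toxicity resolves". Related Grade 4 toxicity leads to withdrawal from study medication. Section 8.1 allows an individual's blind to be broken on several grounds, one of them being that, in the safety monitor's view, "knowledge of the identity of the study drug is essential to appropriately manage an adverse event".

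**The concern.** The halt in 15.2 needs two things: an SMC determination that the event is an SAE, and knowledge that the patient was on active drug. The plan gives the SMC no dated route to either. The bodies that do hear quickly are not given the halt.

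This matters because section 1.4 says the drug has not yet been used in children, and section 3.2 admits patients from age 4. An enrolment halt protects people who have not yet been dosed. Patient-level measures such as dose reduction or withdrawal protect only the person who already had the event. If the halt cannot be triggered promptly, the next child may be randomised while the first case is still unknown to the committee that owns the decision.

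**Working it through.** The plan states no figure on this point, so the main check is a comparison of texts.

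**Step 1. Who hears of an SAE, and who can act.**

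| Body | Told of an SAE | Stated power | Assignment |
|---|---|---|---|
| ISSM | Within 48 h (sections 8, 17) | Relatedness for the sponsor; consultation, further studies, withdrawing the patient | Its view is one ground for unblinding (8.1) |
| IRB and Clinical Director | Within 7 days (17) | IRB reviews before restart (15.2); no halt trigger | Not stated |
| SMC | No route or deadline stated | Enrolment halt and study stop (15.2) | Review is blinded (15.1) |

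The first two rows have the information without the trigger. The third has the trigger without a stated route to the information.

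**Step 2. Follow one SAE on active drug through the text.**
1. The investigator informs the ISSM within 48 hours, and the IRB and Clinical Director within 7 days.
2. The ISSM may intervene for that patient. The blind may be broken under 8.1, but this is permissive and not tied to 15.2.
3. If the blind is broken, nothing says that the assignment goes to the SMC.
4. The SMC must determine the SAE before enrolment halts. No text sends it the case, and no ad hoc review is described. The next stated contact is the scheduled review.

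So a mandatory rule rests on one unstated step (informing the SMC) and one discretionary step (unblinding).

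**Step 3. When the first scheduled SMC review falls.** Inputs from sections 4.1.1 and 4.5.2:
- Titration: 9 to 15 days.
- Each phase: six months, plus or minus 2 weeks.
- Washout: 9 weeks, plus or minus 2 weeks. Section 4.1.1 also describes it as a 9-day taper plus at least 7 drug-free weeks.

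With a month of 30.44 days, six months is 182.6 days, or 168.6 to 196.6 over the window. Time from a patient's first dose to the end of Period 2 = titration + Period 1 + washout (+ second titration, if counted outside the washout) + Period 2.

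- Nominal: 9 + 182.6 + 63 + 182.6 = 437.2 days = 14.4 months.
- Nominal, second titration after the washout: 9 + 182.6 + 63 + 9 + 182.6 = 446.2 days = 14.7 months.
- Shortest, 7-week total washout: 9 + 168.6 + 49 + 168.6 = 395.2 days = 13.0 months.
- Shortest, 9-day taper plus 49 drug-free days: 9 + 168.6 + 58 + 168.6 = 404.2 days = 13.3 months.
- Longest: 15 + 196.6 + 77 + 15 + 196.6 = 500.2 days = 16.4 months.

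Even if all six subjects started on the same day, the review would come at least 13.0 months after the trial's first dose, given full-length periods.

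**Step 4. Sensitivity to the meaning of completion.** Section 3.1 replaces only those who leave before 3 months of the second phase. If completion in 15.1 were read that loosely, the 13.3-month case becomes 9 + 168.6 + 58 + 91.3 = 326.9 days = 10.7 months. The wording of 15.1, which names both periods, favours the full-length reading.

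**The case against.** The best defence is that the halt is triggered by an event and not by a meeting date. Section 15.1 says what monitoring will include, which is not an exclusive list, and the SMC's remit over adverse events and safety reports could cover a single case. Section 15.2 itself contemplates breaking the blind, and blinded aggregate review is compatible with unblinding one case. Section 8.1 is also broader than case management: it extends to non-serious, expected or unrelated events and to regulatory requests. An SAE reaches the sponsor's medical monitor in 48 hours and the IRB and Clinical Director within a week. The NINDS monitoring SOP cited in section 16, and the reporting terms agreed with the sponsor mentioned in section 17, may fill the gap. The ISSM might also sit on the SMC.

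Much of this stands. Oversight of the affected patient is prompt, and nothing forbids the SMC from acting early. But a remit is not a route, and none of the faster bodies is given the halt. Names are removed, so overlap between ISSM and SMC can be neither shown nor excluded. Overlap would shorten the route but would not create a duty to unblind for the halt.

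Three stronger readings are tempting and are not supported:
- That the timing of the first SMC review is stated inconsistently. Only 15.1 dates it. Sections 8 and 17 mention an annual SMC meeting merely as an occasion for reporting nonserious events to the ISSM, which fits the yearly reviews in 15.1.
- That enrolment would continue for 13 to 16 months after an SAE. Those figures describe the first scheduled review. They do not measure a delay to the halt.
- That the halt is impossible because the SMC is blinded. Section 15.2 anticipates unblinding. What is missing is a requirement and a recipient.

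**Conclusion.** The concern holds as a gap in how the halt and stop rules are made to work. Both are SMC decisions, while the stated SAE routes bypass the SMC and the unblinding that the halt needs is neither required nor directed to it. Followed literally, the plan would let new patients, including children, be enrolled after an SAE on active drug.

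The delay to a halt and the number enrolled meanwhile cannot be quantified, because the documents give neither an accrual rate nor an SAE rate. The figure that can be given is separate: the first scheduled SMC review comes at least about 13 months, nominally 14.4, after the sixth completer's first dose. It assumes full-length periods.

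The conclusion rests on the protocol text as available, without the monitoring SOP or any SMC charter. Because patient-level oversight is in place, this is a change that should be made and not a reason to regard the trial as unmonitored.

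**What to change.** 1. **Route (sections 8, 15.2, 17).** Copy each SAE sent to the ISSM within 48 hours to the SMC for ad hoc review, or authorise the ISSM to halt enrolment pending SMC review. State whether seizure hospitalisations are included, since section 17 can be read either way.
2. **Assignment (sections 8.1, 15.2).** For such an SAE, have the NIH Pharmacy, which holds the schedule under 4.5.1, disclose that patient's assignment to the ISSM or SMC only, as a stated exception to blinded review in 15.1. In this crossover one disclosure reveals both periods, so examiners and the study team should not receive it.
3. **First review (section 15.1).** Hold it at the earlier of six completers or 12 months after the trial's first dose. With full-length periods the 12-month limit always comes first.

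The cost is amendment wording, occasional ad hoc SMC contact, one earlier meeting and rare case-level unblinding confined to the safety body. A confirmed halt would tell the study team that the case was on active drug, but the present rule has that effect too. Including seizure hospitalisations would raise the number of contacts, since section 1 reports seizures in 45% of patients. Sample size and endpoints are unaffected.
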